1.2. Objectives

To determine whether active HD-tDCS targeting the dominant posterior TPC can improve language performance, increase language network functional connectivity, and improve abnormal patterns of resting state neuronal frequencies and synchronizations.

Specific Aim 1. Determine changes in language performance after 10 HD-tDCS stimulation sessions (QD) lasting 20 minutes at a current intensity of up to 2mA in the left TPC in a randomized, double-blind, sham-controlled, within-subject cross-over study with 20 lvPPA subjects ages 45 years and greater.

Specific Aim 2. Determine the effects of the conditions described in Specific Aim 1 on the resting state Language network-level changes in left TPC functional connectivity between the conditions described in Specific Aim 1.

Specific Aim 3. Determine the effects of the conditions described in Specific Aim 1 on the neuronal frequency distribution and connectivity measures associated with the left TPC as assessed by MEG.

1.3. Outcome Measurements

The following outcome measurements will be used to test our proposed hypothesis:

- **Primary outcome measures:** Language performance as assessed at baseline and post-stimulation procedure (time frame: 2 weeks)
- **Secondary outcome measures:** Language network resting state changes after stimulation procedure (time frame: 2 weeks)
- **Tertiary outcome measures:** Resting-state neuronal frequencies and synchronizations changes after stimulation procedure (time frame: 2 weeks)

1.4. Impact of the Proposed Study

Currently, no FDA-approved therapy exists for IvPPA despite it being the most prominent cognitive impairment in approximately 27% of patients with early onset Alzheimer's Disease (Mendez et al., 2012). If this mechanistic approach is successful, we will lay a conceptual framework for the future development of optimal neuromodulation avenues for the rehabilitation of multiple neurodegenerative aphasias and other related conditions. We hope the technique will effectively enhance language production for this population.

2. BACKGROUND AND SIGNIFICANCE

2.1. Background

IvPPA is a neurodegenerative condition with no known effective treatment despite its relatively common occurrence in patients with AD and its associated catastrophic effects on work and home life. The disorder is typically characterized by word retrieval difficulties, word and sentence repetition deficits, and overall, by a type of language impairment that leads to a disturbance of the phonemic buffer for words (Meyer et al., 2015). Alzheimer's disease is the most common underlying neuropathology, and in accordance with the role of the posterior perisylvian region in phonological processing (Pillay et al., 2014), focal degeneration of the dominant posterior TPC is the most frequently identified pattern of brain involvement (Gorno-Tempini et al., 2008).

With the advent of tDCS as a promising therapeutic and rehabilitation tool in both post-stroke and neurodegenerative aphasias, it seems likely that these conditions will differ in their optimal neuromodulation approach as a direct result of their distinct underlying pathophysiologic mechanisms: Stimulation of spared perilesional and contralateral areas in the former, and of disease-specific and growingly inefficient brain regions in the latter. Our overall scientific premise is strongly supported by the existing scientific literature, with stroke-related studies showing major neuroanatomical reorganization after the initial injury (Dancause et al., 2005; Abel et al., 2015), and PPA studies revealing early reductions in language-specific effective connectivity and relatively rapid neurodegenerative changes, two findings consistent with the absence of any major reorganizational changes of brain functional networks (Sonty et al., 2007; Rogalski et al., 2011). Despite the soundness of the previously discussed models, all published studies of tDCS in PPA have relied on the broad stimulation of left hemispheric structures using conventional montages, and none of them have sought to use HD-tDCS to focus the stimulation on the more discretely affected brain areas that typify the different PPA variants. (i.e. left TPC in IvPPA, the left Inferior Frontal Gyrus (IFG) in the non-fluent/agrammatic variant, and the left temporal pole in the semantic variant). Correspondingly, an additional element of our overall scientific premise is the fact that HD-tDCS as a technique, can increase current focality and intensity (Datta et al., 2009; Muthalib., 2017). This focality is robust to tissue (modeling) parameters (Datta et al., 2012), and clinical neurophysiological studies have confirmed the focal current delivery (Edwards et al., 2013). Even though no published literature exists on the use of HD-tDCS in the PPA population, its feasibility, tolerability, and its non-inferiority to tDCS have been documented in patients with chronic post stroke aphasia (Richardson et al., 2015). HD-tDCS has also been shown to produce longer lasting after-effects when compared to conventional tDCS (Kuo et al., 2013), and others have already speculated about its potential role in the rehabilitation of neurocognitive impairments resulting from localized brain injury (Hogeveen et al., 2016).

Despite its promise for the treatment of PPA, knowledge of its mechanism of action and a demonstration of its therapeutic effectiveness in this population are still critically needed. In the absence of such knowledge, realization of the therapeutic potential of this cutting-edge technique will likely remain difficult, not only in the case of PPA, but also for the treatment and rehabilitation of other related neurodegenerative conditions.

2.2. Significance

If this mechanistic study succeeds, we will be able to **1)** provide conceptual proof that language performance can be improved by targeting specific dysfunctional neural networks during the clinical phase of disease. **2)** determine whether stimulation intervention reaches specific neural network targets and assess the network level responses; **3)** predict if the network activity modulation can concurrently improve language performance; and **4)** provide essential information needed to prepare future pivotal device trials.

3. RATIONALE

3.1 Scientific Premise

Aim #1. Evaluate the therapeutic efficacy of HD-tDCS. Anodal (positive) tDCS appears to increase both the amount and the speed of learning by promoting mechanisms of long-term potentiation (Fritsch., 2010). From a behavioral perspective, these changes in synaptic activity seem to outlast the initial period of stimulation only when the stimulation is delivered 'online' during a behavioral training task (Monti et al., 2008; Baker et al., 2010; Marangolo et al., 2013), and when compared to the 'offline' method, only 'online' tDCS was capable of reducing vocal response times in a study of elderly adults (Fertonani., 2014). These findings are in support of a pivotal part of our scientific premise: that 'online' HD-tDCS is preferable in elderly persons with aphasia.

Only a small number of tDCS studies exist in the the PPA population; some excluded the lvPPA subpopulation altogether (Cotelli et al., 2014; Teichmann et al., 2016) and another included lvPPA patients, but with what we believe are relative weaknesses in its design: The use of a conventional tDCS montage without individualized modelling of current delivery, the use of a 'locked' target site without consideration of the specific PPA variant at hand, and a relatively short 2-month "wash out" period as evidenced by the persistence of behavioral gains at the 2-month follow up (Tsapkini et al., 2014). An additional small number of studies that included lvPPA patients have been published, all of them relying on the use of conventional tDCS, a single stimulation target for all PPA subtypes, or the absence of a sham condition for comparison (e.g. McConathey et al., 2017; Hung et al., 2017). Based on the support from the discussed studies our scientific premise is that tDCS when combined with language training interventions can improve language performance in PPA. Nevertheless, what remains unknown are the effects of using 'online' HD-tDCS when tailored to each PPA variant and guided by the individualized modelling of target sites.

Aim # 2. Identify the effects of HD-tDCS on language network functional connectivity. We hypothesize that tDCS is able to modulate abnormal neuronal processing in patients with aphasia as measured by fMRI. This premise is supported by a recent study of post-stroke aphasia in which patients named pictures of common objects during fMRI and concurrently received anodal or sham stimulation to the left primary motor cortex. In this experiment anodal tDCS selectively enhanced the activity in a larger language-related network, but not in other task-related components (Darkow et al., 2017). Of note, the authors themselves mentioned that the use of conventional tDCS (and not HD-tDCS) made it impossible to dissect the exact source of the neural modulation. In the specific case of PPA, all PPA syndromes are associated with distinctive functional neuroanatomical profiles of abnormal language processing relative to healthy older individuals (Hardy et al., 2017). The syndromic signatures found in this particular study were in accord with prior predictions and as expected, the logopenic variant was characterized by decreased activation of the posterior superior temporal cortex that correlated with performance on post-scan behavioral testing. What remains lacking is knowledge of the effects of tDCS in general, and HD-tDCS in particular, on measures of brain functional connectivity in the PPA population.

[figure not shown]
Aim # 3. Determine the effects of HD-tDCS on spontaneous neuronal oscillatory patterns. tDCS can reshape brain networks and increase global connectivity in healthy adults as measured by MEG (e.g. Garcia-Cossio et al., 2016). In the case of PPA a recent MEG study demonstrated a distinct spatiotemporal pattern of altered functional connectivity that was unique to each individual variant (Ranasinghe et al., 2017). What remains to be elucidated is the effect that HD-tDCS has on these neurophysiological signatures of network-specific neuronal dysfunction.

4. STUDY DESIGN

4.1. Overall Design

This study will test our hypothesis that HD-tDCS will improve performance on language tasks by increasing functional connectivity and by regulating abnormal neuronal oscillatory patterns. The language performance and functional connectivity changes will be determined in a randomized, double-blind, sham-controlled crossover manner, in which a stimulation of up to 2mA in the targeted cortical tissue or sham is administered to 20 IvPPA subjects age 45 years and older. The order of treatments is counterbalanced in a within-subject crossover design, as illustrated in Fig. 2 below. In brief, study participants will receive sham during one treatment period and stimulation during the other treatment period.

Figure 2. Study Design and tDCS Treatment Protocol

The Screening Visit includes medical history, Language Assessment battery, MRI safety screening, and TMS Neuronavigation. Visit 1 (Baseline) will include fMRI and MEG. Additionally at Visit 1, and for 9 additional days in a two-week period (Tx Period 1), each subject will undergo real stimulation or sham and simultaneous word and non-word reading and repetition tasks. At the end of Tx Period 1, a 16-week washout period begins. After the first 8 weeks of the 16-week washout period, subjects return for Assessment Visit 1 where they receive the Language Assessment battery, including the reading and non-word repetition tasks tested at baseline, and 'trained' during each of the stimulation sessions. After the 16-week washout period, Tx Period 2 begins. Subjects undergo stimulation or sham and the simultaneous word and non-word reading and non-word repetition tasks for 10 days over a two-week period. Eight weeks after the end of Tx Period 2, subjects receive the Language Assessment Battery at Assessment Visit 2, which is the last study visit.

An unblinded member of the study team having no contact with the study subjects will randomize them to the treatment conditions, while the language assessment battery of tests will be delivered by a blinded member of the study team. The language training exercises used during each tDCS session as well as the tDCS intervention itself will be delivered by a blinded, qualified and formally tDCS-trained member(s) of the study team.

Data safety is monitored by three data safety monitoring board (DSMB) members who are not related to the study.

4.2. Inclusion and Exclusion Criteria

Inclusion Criteria

- Diagnosed with IvPPA subtype, defined as either clinical IvPPA or imaging-supported IvPPA in accordance with the most recent diagnostic criteria (Mesulam., 2001; Gorno-Tempini et al., 2011).
- Fluent in English.
- 45 years of age or older (Individuals with IvPPA are extremely rare below this age cut-off).
- Structural brain MRI done within the 3 years prior to enrollment.

Exclusion criteria

- Severe cognitive, auditory or visual impairments that would preclude cognitive testing.
- Presence of major untreated or unstable psychiatric disease.
- A chronic medical condition that is not treated or is unstable.
- The presence of cardiac stimulators or pacemakers
- Any metal implants in the skull
- Contraindications to MRI
- History of seizures
- History of dyslexia or other developmental learning disabilities.

4.3. Subject Recruitment

To enroll a total of 20 study participants, we anticipate pre-screening and approaching about 50 IvPPA patients who are seen in the MCW Neurology clinics and the MCW Geropsychiatry clinic for standard care. These patients will range in age from 45–85 years. Recruitment efforts will be conducted exclusively in the MCW Neurology and Geropsychiatry clinics initially but may be expanded to include the greater metropolitan Milwaukee, WI area if needed. The Medical College of Wisconsin (MCW) Dementia Research Team has extensive experience recruiting patients from the clinic and the Milwaukee community, using flyers, press releases, and community presentations.

5. STUDY VISITS AND PROCEDURES

5.1. Schedule of Visits

A **screening (Visit -1)** session will be conducted. This could take place after a routine clinic visit, or by phone, to perform the Informed Consent (IFC) discussion, review inclusion criteria, collect demographics and basic medical history, and begin MRI safety screening. The Language Battery will also be completed as part of the screening visit. Additionally (in the case of those meeting criteria), patients might visit the Tosa Health Center or Medical College of Wisconsin for stimulation planning. This would entail the use of a Transcranial Magnetic Stimulation (TMS) neuronavigation system. The Language battery and TMS can occur on two separate days prior to the first treatment visit of Treatment Period 1. Subjects will also be invited to **baseline (Visit 1)**. At baseline, the study team will complete fMRI and MEG scans and randomize participants to a treatment group. Procedures within Visit -1 and Visit 1 may be completed in any reasonable order, and may overlap, up to 3 months prior to the first treatment visit of Treatment Period 1. At **Visit 1**, subjects will receive tDCS while simultaneously completing the reading and repetition “trained tasks. Subjects will then return for 9 additional **treatment sessions (Visits 2-10)** where they will receive stimulation or sham, along with trained task administration. At **Visit 10**, subjects will receive MRI, MEG scans, and the Language Battery. These procedures may be completed one month after the last treatment session of Treatment Period 1. At 8-weeks from the last Treatment Period 1 visit, subjects will return for the first **assessment session (Visit 11)**, in which the Language battery, including the trained tasks will be repeated. Subjects will then return 8 weeks later to begin the second series of treatments (**Treatment Period 2, Visits 12-21**) and receive MRI, MEG, and Language Battery on visits 12 and 21. MRI, MEG, and the Language battery will be completed no greater than 3 months prior to the first treatment session of Treatment Period 2, then again no greater than one month after the final treatment session of Treatment Period 2. At each visit during Treatment Period 2, subjects will receive the cross-over treatment (either sham or stimulation) while simultaneously completing the reading and non-word trained tasks. The final

assessment session (**Visit 22**) will be conducted 8 weeks post Treatment Period 2. The Language battery, including the trained tasks, will be repeated at this final study visit.

Refer to Table 1 for a schedule of study procedures.

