7.10. Feedback Mechanism

Evaluation and response to any subject complaints will be reviewed by the DSMB. The IRB will be notified of protocols violations and emergence of unexpected AEs at any time during the study. In addition, a report by the DSMB will be provided to the IRB at the end of the study.

Table 1. Schedule of Study Procedures.

Period	Screen	Treatment Period 1			Assessment 1 ^{ab}	Treatment Period 2			Assessment 2 ^b
Visit	-1	1	2-9	10	11	12	13-20	21	22
Visit window	-3 months	-3 months	+1 month	+1 month	±1 month	-3 months	+1 month	+1 month	±1 month
Informed Consent	X								
Inclusion/Exclusion Criteria	X								
Demographics	X								
Medical History	X								
MRI Safety Screening	X					X			
Language Battery	X ^j		X ^{fh}		X	X ⁱ		X ^{fh}	X
Training Tasks		X	X	X	X	X	X	X	X
fMRI ^c		X ^g		X ^h		X ⁱ		X ^h	
MEG		X ^g		X ^h		X ⁱ		X ^h	
Randomization		X							
tDCS		X	X	X		X	X	X	
Phone Follow Up/					X				

Visit Reminder ^d									
Adverse Events ^d		X	X	X	X	X	X	X	X
TMS Neuronavigation (for stimulation planning) ^e	X ^j								

^a Assessment 1, Visit 11 occurs in the middle of the 16-week washout period.

^b In the case of early termination, Assessment Visit procedures will be performed.

^c Subjects will undergo mock scanner training. If a subject has been previously engaged in MRI as part of research, the subject may be excused from mock scanner training.

^d Phone Follow-Ups will be conducted during the 16-week washout period. They will be conducted 4 weeks post Treatment Period 1, 1 week prior to Assessment Visit 1, and 1 week prior to Treatment Period 2. AE review will be completed, and reminders for upcoming visits provided.

^e TMS Neuronavigation will occur at the investigators discretion.

^f Language assessment sessions will be conducted after Treatment periods 1 and 2 (visit 10 for period 1 and visit 21 for period 2).

^g These procedures can occur on 2 or more separate days, but within 3 months before the first treatment session of Treatment Period 1. They may overlap with Visit -1 procedures.

^h These procedures can occur on 2 or more separate days, but within 1 month after the last treatment session of Treatment Period 1 or the last treatment session of Treatment Period 2.

ⁱ These procedures can occur on 2 or more separate days, but within 3 months before the first treatment session of Treatment Period 2.

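### The period-2 language baseline may be taken up to 3 months before period 2 with no minimum time after period 1, so a compliant baseline can fall at about day 56 of a 112-day washout, or day 20-23 on the literal text

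*Protocol*

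**What the plan says.** Protocol 5.1 gives the nominal timing. After Visit 11, at 8 weeks, "Subjects will then return 8 weeks later to begin the second series of treatments", and participants "receive MRI, MEG, and Language Battery on visits 12 and 21". It then adds a window: "MRI, MEG, and the Language battery will be completed no greater than 3 months prior to the first treatment session of Treatment Period 2". Table 1 repeats it as a minus 3 months window for Visit 12, and footnote i reads "These procedures can occur on 2 or more separate days, but within 3 months before the first treatment session of Treatment Period 2". Both limits count back from period 2. Neither counts forward from period 1, and neither says whether the battery must follow Visit 11.

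For period 1, 5.1 says that screening and baseline procedures "may be completed in any reasonable order, and may overlap, up to 3 months prior to the first treatment visit of Treatment Period 1", and footnote g adds "They may overlap with Visit -1 procedures". Footnote i has no such overlap wording.

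The position of Visit 11 is not stated consistently. Footnote a says "Visit 11 occurs in the middle of the 16-week washout period", and Protocol 4.1 agrees, but the Study Design row of the Protocol Summary lists the interim assessment after the washout. Table 1 also gives Visit 11 a window of plus or minus 1 month.

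The SAP compares percentage change from T0 to T1 under active stimulation with the same change under sham, participant by participant. It assesses each trial period separately to help control carryover and disease progression.

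**The concern.** A washout protects a crossover comparison only if the second baseline is measured when the washout is over. Here the 16 weeks govern when treatment restarts, while the baseline has its own, looser rule. Protocol 3.1 counts a 2-month washout among the weaknesses of an earlier tDCS trial in PPA, because gains were still visible then. The window nevertheless permits a baseline at or before that interval.

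Analysing the periods separately does not repair this, because any residual effect is inside the reference value itself. In an active-first participant, a benefit present at T0 that fades before T1 would lower the sham change and favour stimulation. Language training is given in both conditions, so in a sham-first participant carried-over training gains could lower the active change and act the other way. Because the SAP works within individuals, one early T0 can affect the whole of that participant's comparison. An early baseline would comply with the protocol, so a deviation log would not show it.

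**Working it through.** **Conventions.** Day 0 is the last period-1 session. Months are calendar months: 1 month = 28-31 days, 2 months = 59-62 days, 3 months = 89-92 days. T0, T1 and T2 are taken as the baseline, post-treatment and 8-week batteries of each period. The SAP does not define these labels, but this matches its three timepoints.

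**The plan's own figures.** Participation is 2 + 16 + 2 + 8 = 28 weeks, as in the Protocol Summary. The washout is 8 + 8 = 16 weeks, and 16 × 7 = 112, so period 2 starts on day 112.

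**Reading A: the battery must follow Visit 11.** This is the order in which 5.1 lists events.
- Visit 11 is nominally on day 8 × 7 = 56.
- Day 56 is 112 − 56 = 56 days before period 2, inside the 3-month window and half the washout.
- It is 59 − 56 = 3 to 62 − 56 = 6 days short of 2 calendar months.

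**Reading B: literal text, no order imposed.**
- Earliest T0 = 112 − 92 = day 20 to 112 − 89 = day 23.
- This is 59 − 23 = 36 to 62 − 20 = 42 days before the 2-month point.
- Footnote h allows the post-treatment battery "within 1 month after the last treatment session of Treatment Period 1 or the last treatment session of Treatment Period 2", so T1 of period 1 can be as late as day 28-31. The second baseline could then precede the first outcome by 28 − 23 = 5 to 31 − 20 = 11 days.

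**Early Visit 11.**
- Visit 11 at its early limit is 56 − 31 = day 25 to 56 − 28 = day 28.
- T0 at day 25-28 follows only if period 2 stays at day 112.
- If period 2 instead starts 8 weeks after that visit, as 5.1 words it, it starts on 25 + 56 = day 81 to 28 + 56 = day 84, which is not a 16-week washout. The two statements conflict.

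**Whether a 2-week window alone would be enough.** With period 2 on day 112 it runs from day 98 to day 112. The latest permitted Visit 11 is 56 + 28 = day 84 to 56 + 31 = day 87, so the order holds with 98 − 87 = 11 to 98 − 84 = 14 days to spare. With a day 81-84 start, the same window would open on 81 − 14 = day 67 to 84 − 14 = day 70. A minimum counted from period 1 is therefore needed as well.

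No bias can be computed, because the documents give no rate at which an effect decays.

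**The case against.** The strongest reply is that week 16 is the scheduled time and the early dates are artefacts of a scheduling allowance. Much of this stands. Day 20-23 requires a Visit 12 procedure before Visit 11, and possibly before the period-1 outcome, which was probably not intended. Day 56 is close to 2 months. It would also put two batteries next to each other, at up to 160-170 minutes if done together (2 × the 80-85 minutes of listed test times). Separate item sets or versions per period for naming, phonological memory, rhyme, reading comprehension, MoCA and the trained items limit item-specific carryover, and the NAB alternative for the speech sample has two versions. What remains is a possible general language effect, plus fluency, digit span and the Cookie Theft picture, for which no period-specific version is stated.

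A reader might go further and infer three things that the documents do not support:
- That baselines were in fact taken early. No dates are given.
- That the results favour stimulation. The two treatment orders can push in opposite directions, and the mechanism needs an effect that is present at T0 and fades before T1.
- That carryover at 2 months has been shown for this battery. The earlier trial used conventional tDCS with spelling therapy. It supplies the protocol's own argument about washout length, not evidence about these tests.

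The 3-month age limit is also not peculiar to period 2, since the period-1 baseline has it too. Only the carryover part is.

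What the reply does not remove is that no rule puts a floor under the period-2 baseline, and even the favourable reading permits half the washout.

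**Conclusion.** The point holds as a defect in the timing rule. The period-2 language baseline has no minimum interval after period 1 and can comply at about day 56 if it follows Visit 11, or at day 20-23 if no order is imposed. The first is the more plausible reading; the second shows that the order needs to be stated. Day 25-28 should not be cited as a plain limit, because it depends on holding period 2 at day 112 after an early Visit 11, against the 8-week wording in 5.1.

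The figures assume that period 2 starts exactly on day 112; a later start moves the literal limit later. The arithmetic and the absence of a stated minimum are certain. Which reading the site followed, whether any baseline was early, and the size and direction of any bias cannot be determined from the documents. The rule should be corrected and the dates reported, but this is not grounds for discounting the results.

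**What to change.** **Protocol text, and any later trial.** Keep the 3-month window for MRI and MEG. For the period-2 Language Battery require all three of the following:
- it follows Visit 11;
- it falls within a short window before the first period-2 session, for example 2 weeks;
- it is not before a stated minimum counted from the last period-1 session, for example week 14 (day 98).

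The lengths are judgements. The minimum can be met only if period 2 starts on or after it, so the passages on Visit 11 and the start of period 2 must be reconciled first: the Protocol Summary, 4.1, 5.1, and Table 1 with footnote a.

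**Data already collected** (the SAP is written in the past tense). List the actual T0, T1 and T2 dates for each participant and period. Mark any participant whose period-2 T0 was early, and interpret that participant's active-versus-sham comparison as potentially affected by carryover. Simply dropping such a T0 tells little, because it deletes that person's comparison and changes no other. Use the Visit 11 battery, set against the period-1 baseline, to show whether a period-1 change persisted at about week 8.

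**Separate wording point.** Section 6.2 places the post-treatment data on the final day of each treatment period, while 5.1 and footnote h allow up to 1 month afterwards. These should say the same thing.

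**Cost.** For collected data, a date listing and a short note per marked participant. For the protocol, less scheduling flexibility and, where the battery is separated from the scans, possibly an extra trip for a session of about 80-85 minutes (10 + 6 + 5 + 10 + 10 + 4 + 10 + 25 to 30, trained tasks included; reading comprehension has no stated time).
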